## **6.4** Subject Disposition and Characteristics

- (1) Subject disposition
  - The number of subjects randomized to each group will be tabulated in a manner so as to clarify attribution of subjects in each analysis set, and a summary and a list of subjects excluded from each analysis set will be provided with the reason for exclusion.
    - The presence or absence of important protocol deviations will be tabulated among the all enrolled patients. The types of deviations will be displayed together with the number of subjects.
    - The presence or absence of and the reasons for study discontinuation will be summarized among the all enrolled patients.
- (2) Subject characteristics
  - For each analysis set, excluding all enrolled patients, distribution of the following subject and disease characteristics will be summarized.
    - Demographic variables: Gender, race, age, age category (≥5 years and <7 years, and ≥7 years), height, body weight, presence or absence of previous medical history, and presence or absence of complication.
    - 2) Subject characteristics variables: Previous medical history, complication, presence or absence of diagnosis of DMD, diagnosis of DMD, presence or absence of the history of steroid use, history of steroid use, presence or absence of history of surgery, history of surgery, rehabilitation status, presence or absence of fitting of splint/insole, presence or absence of the use of wheel chair, 6MWD test, time to rise from the floor test, timed 10-m walk/run test, Timed Up & Go test

## **6.5** Dosing Information

The following analyses by treatment group will be performed in treated patients:

- (1) Dosing Information
  - Summary of the total dose and total duration of administration for each subject will be shown.
     Analyses will also be conducted for the PPS.
- (2) Completed administration
  - Summary statistics of the dosing rate of TAS-205 will be calculated. The dosing rate will be calculated by the following formula.

#### Actual number of tablets

Dosing Rate =  $\frac{1}{(Criteria number of tablets (Administration number of days^{*1} \times Tablets/dose \times n Dose/day))^{*2}}$ 

\* To be induced from Day of last administration - Day of first administration + 1, because there is an allowable period for the day of last administration. The number of days will be calculated by subtracting 0.5 from the number of days of administration if administration is started in the evening on the day of first administration, and also by subtracting 0.5 from the number of days of administration if administration is terminated in the morning of the day of last administration.

\* If the dose is reduced during the study, the denominator for the dosing rate will be the sum of the number of days of administration before dose reduction  $\times$  tablets/dose before dose reduction  $\times$  twice/day and the number of days of administration after dose reduction  $\times$  tablets/dose after dose reduction  $\times$  twice/day.

- The Dosing Completed Rate of TAS-205 (proportion of subjects who were administered TAS-205 as in a specified schedule) will be calculated. The subjects will be the patients for whom the dosing rate is lower than 100%.
  - The presence or absence of concomitant medication and concomitant therapy (other than steroids) will be tabulated.
  - The presence or absence of the use of steroids will be tabulated.

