- 14. Administration start day (Day 1): The administration of the investigational product will be started after dinner on the end day of pooled urine (within 14 days after enrollment); however, if it is not possible to perform the efficacy evaluation (corresponding to Note 1) due to an adverse event or any other reason, or to start the investigational product administration on the end day of pooled urine, the administration may be started after dinner within the end day of pooled urine + 2 days (within up to 16 days after enrollment) (the actual administration start day will be designated as Day 1). The increase in the number of hospitalization days due to the delay of the administration start day (excluding prolonged hospitalization due to inpatient treatment) will not be assessed as a serious adverse event.
- 15. Clinical assessments in the baseline period: Performed no later than administration on the investigational product administration start day (administration after dinner on Day 1), in principle
- 16. Discontinuation test: Performed at the first visit after discontinuation whenever possible (safety endpoints will be evaluated)
- 17. Efficacy endpoints on the end day of administration: Evaluated after the last dose of the investigational product (standard: administration after breakfast on Day 169)
- 18. Follow-up test: Performed 21 days after the last day of the investigational product administration (standard day ± 7 days is permissible).
- 19. Endocrinology at the follow-up test: Performed only if an abnormal change (adverse event) is observed in the test on the discharge day for the 3rd hospitalization (standard: Day 169). Such an endocrinological test will be performed around 8:00 to 10:00 am on the follow-up test day. For subjects who visit the study site from afar, a stay at night before the follow-up test day (stay at or outside the study site; planned hospitalization or stay at a nearby facility) will be considered to collect blood within the specified time window whenever possible.

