# 7. Method of Administration

Subjects will receive the investigational product orally twice daily for 24 consecutive weeks, with the first dose after dinner on Day 1 and the last dose after breakfast on the efficacy evaluation day at Week 24, until the end day of the study or the subjects meet any of the discontinuation criteria specified in Section 4.3.

The administration of the investigational product will be started within 14 days after enrollment (Day 1) (if Note 14 in Table 1 is applicable, the administration may be started within up to 16 days after enrollment). Any suspended or missed dose during the administration period will not be administered later than administration after breakfast on the efficacy evaluation day at Week 24.

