# 13.1.3.5 Current Administration

The following analyses by treatment group will be performed in subjects administered the investigational product:

- (1) Current administration
  - Summary of the total dose and total duration of administration for each subject will be shown.
- (2) Completed administration
  - Summary statistics of the administration rate of TAS-205 will be calculated.
  - The rate of completed administration of TAS-205 (proportion of subjects who were administered TAS-205 as in a specified schedule) will be calculated.
  - The presence or absence of and the reasons for study discontinuation will be summarized.

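### SAP 6.5 defines the Dosing Completed Rate as the share of boys dosed on schedule, then assigns it to boys whose dosing rate is below 100%

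*SAP*

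**What the plan says.** Protocol 13.1.3.5 plans the figure in one line: "The rate of completed administration of TAS-205 (proportion of subjects who were administered TAS-205 as in a specified schedule) will be calculated". SAP 6.5 takes over the same definition under the name Dosing Completed Rate. It then adds a sentence that the protocol does not have: "The subjects will be the patients for whom the dosing rate is lower than 100"%.

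The dosing rate itself is defined just above, also in SAP 6.5. It is the actual number of tablets divided by a criterion number, which is days of administration × tablets per dose × doses per day. Two footnotes govern the denominator:

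- Days are "To be induced from Day of last administration - Day of first administration + 1", less half a day for an evening start and half a day for a morning finish.
- The second footnote begins "If the dose is reduced during the study, the denominator for the dosing rate will be the sum of the number of days" and goes on to weight the days before and after a reduction by the tablets per dose in force in each stretch.

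The population is set at the head of the section: "The following analyses by treatment group will be performed in treated patients". No other section of either document restates or corrects the rule.

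**The concern.** The two sentences pick out opposite groups. The definition asks for the "proportion of subjects who were administered TAS-205 as in a specified schedule", while the added sentence names the boys whose tablet count fell short. A programmer who works from the text has to discard one of them.

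The rate is reported by treatment group. The regimen runs to 24 tablets per dose, twice daily, in the heaviest weight band (Protocol Table 7.1.1-1), and the high dose had not been given in a clinical study before (Protocol 1.3.2). Readers will look at this line to see how many boys followed the regimen. Under the plainest reading of the added sentence, the printed value would look credible, and the group with poorer adherence would show the higher completed rate.

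**Working it through.** The documents state no completion percentage, so there is no figure to reproduce. The check applies the SAP formula to the planned schedule.

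**1. Length of a full course.** Protocol section 7 has dosing run "with the first dose after dinner on Day 1 and the last dose after breakfast on the efficacy evaluation day at Week 24". Table 1, note 17, puts the standard last dose on the morning of Day 169.

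Days = 169 − 1 + 1 − 0.5 − 0.5 = 168. Doses = 168 × 2 = 336.

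**2. What a rate below 100% means.**
- One whole dose missed: 335/336 = 99.7%.
- One tablet missed at 4 tablets per dose: 1,343/1,344 = 99.93%.
- One tablet missed at 24 tablets per dose: 8,063/8,064 = 99.99%.

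Protocol 7.1.2.2 treats vomited or partial doses as full doses. If the tablet count follows that rule, a partly taken dose may not lower the rate, but a wholly missed dose always does. In either case a rate below 100% marks a shortfall against the schedule.

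**3. The three readings.** Take n = 11 per group (SAP section 2) and let k be the number of boys below 100%. The values of k are assumptions, because the documents give none.

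| k | Definition, (11 − k)/11 | Sentence as numerator, k/11 | Sentence as denominator, 0/k |
|---|---|---|---|
| 0 | 100.0% | 0.0% | undefined |
| 1 | 90.9% | 9.1% | 0% |
| 3 | 72.7% | 27.3% | 0% |
| 8 | 27.3% | 72.7% | 0% |

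The numerator reading is always the complement of the defined rate. The two would agree only at k = 5.5, which cannot occur. The denominator reading agrees with the definition only if all 11 boys are below 100%.

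**4. Would reversing the inequality be enough?** No. The SAP denominator stops at the last administration and is rebased after a reduction.
- A boy who stops on the morning of Day 57 with nothing missed has 57 − 1 + 1 − 1 = 56 days, or 112 doses. His dosing rate is 112/112 = 100%, on 112/336 = 33.3% of the planned doses.
- A boy on 8 tablets per dose, halved after 84 days with nothing missed, takes 84 × 8 × 2 + 84 × 4 × 2 = 2,016 tablets. His dosing rate is 2,016/2,016 = 100%, on 2,016/2,688 = 75% of the planned tablets.

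**5. Would a fixed count of 336 doses work?** No. The Week 24 evaluation may fall from Day 162 (admission on Day 160, evaluation two days later; Protocol Table 1, note 1) to Day 178 (Protocol 3.2.2.2).
- Day 162, nothing missed: 161 × 2 = 322 doses, and 322/336 = 95.8%.
- Day 178, nothing missed: 177 × 2 = 354 doses, and 354/336 = 105.4%.
- Day 178, 18 doses missed: 336/336 = 100%.

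A fixed count would misclassify all three boys.

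**The case against.** The strongest defence is that the SAP gives the right definition in the sentence immediately before, so the addition is probably a drafting or translation slip for not lower than 100%. Output layouts are left to a separate report analysis plan (SAP 8.2), which may settle the matter. Tolerance of the tablet load also shows in outputs that this sentence does not touch: dosing-rate summary statistics, total dose and duration (SAP 6.5), reasons for discontinuation (SAP 6.4), and adverse events leading to suspension, reduction or discontinuation (SAP 6.2.2).

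Most of this stands as a limit on importance. It does not remove the contradiction. The words are complete and spelled out, so this is not a lost symbol, and the SAP is where the derivation is specified.

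Three stronger inferences are tempting, and the documents do not support them:

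- *The reported rate is certain to be reversed.* The SAP does not say whether its sentence fixes the numerator or the denominator, and only the first gives a reversal.
- *A key feasibility result is lost.* The stated objectives are efficacy, safety, dose relationship and pharmacodynamics. Feasibility appears as the basis for the sample size, not as an outcome.
- *The size of the error can be forecast.* If every dose were taken independently with probability 0.99, 0.995 or 0.999 and nobody stopped, the share at 100% would be 0.99^336 = 3%, 0.995^336 = 19% or 0.999^336 = 71%. The arithmetic is right, but none of those assumptions comes from the documents.

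**Conclusion.** Wrong as written. The added sentence contradicts the definition it is meant to apply. It leads either to the non-completion rate or to a value that is 0% or undefined. That conclusion does not depend on any assumed adherence; only the example of 27.3% against 72.7% rests on the assumed 3 of 11 boys.

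The reach is small. One descriptive compliance figure per group is affected. The primary analysis, the per-protocol exclusion below 70% and the dosing-rate summary statistics do not use it. It is worth correcting because the wrong number would not look wrong, and because simply reversing the inequality would still count early stoppers and boys with a reduced dose as completed.

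**What to change.** Replace the sentence in SAP 6.5 with:

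> Completed subjects are treated patients who reached the Week 24 evaluation and whose dosing rate through their actual last scheduled dose is not lower than 100%; the denominator is all treated patients in the group.

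Requiring the Week 24 evaluation removes the early stoppers. Counting to each boy's own last scheduled dose respects the permitted visit window, which a fixed 336-dose count does not.

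Add one further sentence saying whether a boy with a dose reduction counts as dosed on schedule, since the rebased denominator otherwise decides this silently. That is a reporting definition for the sponsor to choose and does not touch the reduction rule itself.

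The cost is two sentences in the SAP, settled before the key codes are broken. The change needs no new data and leaves every other analysis as it is.

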## **6.6** Exploratory Analysis

The following analyses will be performed in the PPS. The analysis of %MVI of muscle volume measurement (skeletal muscle CT) will be performed in the lower leg, thigh, and thigh + lower leg.

- (1) 6MWD
  - For the group combining all groups, the correlation coefficients (Pearson and Spearman) of 6MWD at Week 24 and %MVI (%) of muscle volume measurement (skeletal muscle CT) will be calculated.
  - For each group and the group combining all groups, the correlation coefficients (Pearson and Spearman) of the changes in 6MWD at Week 24 and the changes in MVI (%) of the muscle volume measurement (skeletal muscle CT) in both legs and P values for the correlation coefficients will be calculated. In addition, subgroup analysis will be conducted for the following items.
    - Subgroup analysis: Baseline 6MWD ( $\leq$ 350 m, and  $\geq$ 350 m)
  - Analysis of covariance will be performed using the following variables as conditions.
     Objective variable: Change in 6MWD at Week 24
     Explanatory variables: Baseline 6MWD, age, presence or absence of the history of steroid use, baseline %MVI (%) in both legs, and changes in %MVI (%) in both legs at Week 24
     In addition, subgroup analysis will be conducted for the following items.
     Subgroup analysis: Baseline 6MWD (<350 m, and ≥350 m)

  - For each group and the group combining all groups, the correlation coefficients (Pearson and Spearman) of the changes in 6MWD at Week 24 and the change rates of urinary tetranor-PGDM/creatinine concentration ratio and urinary tetranor-PGDM on Day 168 and P values for the correlation coefficients will be calculated. In addition, subgroup analysis will be conducted for the following items.

Subgroup analysis: Baseline 6MWD (<350 m, and  $\geq 350 \text{ m}$ )

- Analysis of covariance will be performed using the following variables as conditions.

Objective variable: Change in 6MWD at Week 24

Explanatory variable: Baseline 6MWD, age, presence or absence of the history of steroid use, baseline urinary tetranor-PGDM/creatinine concentration ratio, and the change rate of urinary tetranor-PGDM/creatinine concentration pay 168

In addition, subgroup analysis will be conducted for the following items.

Subgroup analysis: Baseline 6MWD (<350 m, and  $\geq 350 \text{ m}$ )

- (2) %MVI (%) of muscle volume measurement (skeletal muscle CT)
  - For each group and the group combining all groups, summary statistics of baseline %MVI (%) in both legs will be calculated.
  - For each group, summary statistics of baseline %MVI (%) will be calculated, and 2-sample t-test between groups will be performed. In addition, subgroup analysis will be conducted for the following items.
    - Subgroup analysis: Baseline 6MWD (<350 m, and ≥350 m)
  - For the group combining all groups, the correlation coefficients (Pearson and Spearman) of each %MVI (%) at baseline will be calculated.
  - For each group and the group combining all groups, the correlation coefficients (Pearson and Spearman) of the changes in the %MVI (%) in both legs at Week 24 and the change rates of urinary tetranor-PGDM/creatinine concentration ratio and urinary tetranor-PGDM on Day 168, and P values for the correlation coefficients will be calculated. In addition, subgroup analysis will be conducted for the following items.

Subgroup analysis: Baseline 6MWD ( $\leq$ 350 m, and  $\geq$ 350 m)

Analysis of covariance will be performed using the following variables as conditions.
 Objective variables: Changes in %MVI (%) in both legs at Week 24
 Explanatory variables: Baseline %MVI (%) in both legs, age, presence or absence of the history of steroid use, baseline urinary tetranor-PGDM/creatinine concentration ratio, and the change rate of urinary tetranor-PGDM/creatinine concentration ratio on Day 168
 In addition, subgroup analysis will be conducted for the following items.

Subgroup analysis: Baseline 6MWD (<350 m, and ≥350 m)

- (3) Pharmacodynamic Endpoints
  - For each group and the group combining the low-dose group and the high-dose group, summary statistics of the change rates of urinary tetranor-PGDM excretion, urinary tetranor-PGEM excretion, urinary tetranor-PGDM/creatinine concentration ratio, and urinary tetranor-PGEM/creatinine concentration ratio will be calculated at each time point, and 1-sample t-test using the change rate = 0% as null hypothesis will be conducted at each time point. In addition, subgroup analysis will be conducted for the following items.

Subgroup analysis: Baseline 6MWD (<350 m, and ≥350 m)

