For patients with DMD, no effective treatments are available except for oral steroids, but oral steroids require dose reduction, change in regimen, and even dose suspension in order to manage associated adverse reactions; therefore, a new treatment is highly needed. While no clinical studies to evaluate the efficacy of TAS-205 have been conducted in patients with allergic rhinitis, development of a new treatment for DMD is considered to be highly valuable, and thus a Phase I single- and repeated-dose study in patients with DMD was conducted. In this study, TAS-205 was demonstrated to be highly safe and tolerable in patients with DMD when given at 1.67 to 13.33 mg/kg as a single dose and at repeated doses twice daily for 7 days. TAS-205 also decreased urinary excretion of tetranor-PGDM (total excretion of tetranor-PGDM and tetranor-PGDM/Cre concentration ratio), a marker of PGD2 production, with increasing dose. Significantly increased urinary excretion of tetranor-PGDM in nonambulatory subjects compared with ambulatory subjects when analyzed by ambulatory function as the subject characteristic, as well as higher urinary excretion in patients with DMD aged 8 years or older compared with healthy subjects of the same age and reportedly increased urinary excretion with age suggest involvement of PGD2 production in the development of DMD. In conclusion, it was considered of great significance to evaluate the efficacy of TAS-205 in patients with DMD, and an early Phase II study in these patients was therefore planned.

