### 3.2 Subject Randomization and Blinding

### 3.2.1 Randomization Method

This study is a randomized study.

After providing due explanation to each prospective patient and his legal representative, the investigator or subinvestigator will obtain written informed consent/assent, and then prepare a screening log of patients whose legal representative consented to participate in the study in order to check the patient enrollment in the study. After confirming that the prospective patient is deemed eligible by meeting all of the inclusion criteria and none of the exclusion criteria, all necessary information will be entered the Interactive Web Response System (IWRS) and submitted to the Enrollment Center.

Upon completion of enrollment after confirmation of subject eligibility, the subjects will be randomly assigned to the low-dose group, high-dose group, or placebo group in a ratio of 1:1:1 via IWRS based on a dynamic randomization method (minimization method).

Data will be entered in accordance with the description in the IWRS procedure.

The subjects will be stratified by the following randomization adjustment factors:

- Age (between 5 and 6 years, 7 years or older)
- Presence or absence of concomitant steroid use

The above-mentioned enrollment and randomization will be centrally managed; after completion of the enrollment procedure, each subject will be assigned to a treatment group and given an investigational product number to be initially prescribed (for 6-week administration) by the enrollment system.

The investigational product numbers corresponding to subject randomization will be given and reported to the study site with instructions on the investigational product prescription via IWRS. For more detailed information, refer to the IWRS procedure.

If an investigational product not corresponding to the number given via IWRS is prescribed to a subject in error, the IWRS help desk must be notified immediately. In addition, the cause of the erroneous prescription of the investigational product must be recorded at the study site. If a subject receives the investigational product for a different treatment group due to an error in the investigational product number allocation or prescription, the subject will continue to receive the investigational product for the rest of the study period.

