# 13.1.4 Target Sample Size and Rationale for the Sample Size

Target sample size: a total of 33 subjects (11 subjects for each group)

Given that DMD is a rare disease that allows only limited recruitment of subjects and that this study is primarily intended to evaluate the efficacy of TAS-205 in an exploratory manner, the sample size was determined not statistically, but based on feasibility.

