#### O MMRM

The confidence coefficient for estimation of confidence interval will be 2-sided 95%. In the analysis of MMRM, SAS MIXED procedure will be used as shown in the following SAS code.

proc mixed data = INDATA;

class	ATRTN † (ref='1'[Placebo]) AVISITN † SUBJID † ;
model	$AVAL^{\dagger} = BASE^{\dagger} ATRTN AVISITN ATRTN*AVISITN / ddfm = KR ;$
lsmeans	ATRTN*AVISITN / diff cl alpha = 0.05 ;
repeated	AVISITN / subject = SUBJID type = $UN^{\#}$ ;
estimate	"Low Dose TAS-205 Saturation - Week 12" ATRTN -2 1 1 ‡
	ATRTN*AVISITN $-2\ 0\ 1\ 0\ 1\ 0$ / cl alpha = 0.05;
estimate	"Low Dose TAS-205 Saturation - Week 24" ATRTN -2 1 1 ‡
	ATRTN*AVISITN $0 - 2 0 1 0 1 / cl alpha = 0.05$ ;
estimate	"Placebo vs High Dose TAS-205 - Week 12" ATRTN -1 0 1 ‡
	ATRTN*AVISITN $-100010$ / cl alpha = 0.05;
estimate	"Placebo vs High Dose TAS-205 - Week 24" ATRTN -1 0 1 ‡
	ATRTN*AVISITN $0 - 1 0 0 0 1 / cl alpha = 0.05$ ;
estimate	"High Dose TAS-205 Saturation - Week 12 " ATRTN -1 -1 2 ‡
	ATRTN*AVISITN $-1 \ 0 \ -1 \ 0 \ 2 \ 0 \ / \ cl \ alpha = 0.05$ ;
estimate	"High Dose TAS-205 Saturation - Week 24 " ATRTN -1 -1 2 ‡
	ATRTN*AVISITN $0 - 1 0 - 1 0 2 / cl alpha = 0.05$ ;

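### The SAP 6.6 models relating PGDM change to 6MWD and %MVI change pool three randomised arms without an arm term, so a dose-related drug effect by another route can appear in part as a PGDM–outcome link

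*SAP*

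**What the plan says.** SAP 6.6 specifies three analyses of covariance, all in the PPS, each with five explanatory variables.

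- **6MWD change on muscle change.** After baseline 6MWD, age and steroid history, the list ends with "baseline %MVI (%) in both legs, and changes in %MVI (%) in both legs at Week 24".
- **6MWD change on PGDM change.** "Explanatory variable: Baseline 6MWD, age, presence or absence of the history of steroid use, baseline urinary tetranor-PGDM/creatinine concentration ratio, and the change rate" of that ratio on Day 168.
- **%MVI change on PGDM change.** The outcome is given as "Objective variables: Changes in %MVI (%) in both legs at Week 24". The regressors are baseline %MVI, age, steroid history, the baseline PGDM/creatinine ratio and its change rate.

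None of the lists includes assigned group, and none of these bullets says the model is fitted by group. Elsewhere the SAP names assigned group when it wants it in a model: the MMRM covariates in 6.1, 6.2.1 and 6.3 all begin with it.

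For the same pairs of changes, 6.6 also plans Pearson and Spearman correlations with P values, both within each group and with all groups combined.

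On the drug's effect on the biomarker, Protocol 1.1 states: "TAS-205 also decreased urinary excretion of tetranor-PGDM (total excretion of tetranor-PGDM and tetranor-PGDM/Cre concentration ratio"), with the fall growing as dose increased. Protocol 1.4.2.2 reports the same finding more cautiously, as a suggestion from the data.

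**The concern.** Dose is randomised and the drug is expected to lower PGDM with dose, so PGDM change carries information about the arm. A pooled regression with no arm term mixes two questions: whether boys on a higher dose did better, and whether, among boys on the same treatment, those whose PGDM fell more did better. Only the second is evidence of a link beyond the randomised comparison itself.

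The exploratory objective (Protocol 2.3, SAP 3.1) includes the relationship between urinary excretion and efficacy. A pooled coefficient could be read as support for that link when no such association exists within arms. The combined-group correlations share the problem.

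**Working it through.** **Inputs from the documents.** "Target sample size: a total of 33 subjects (11 subjects for each group"), allocated to "low-dose group, high-dose group, or placebo group in a ratio of 1:1:1". There is no planning effect size or SD to draw on: "the sample size was determined not statistically, but based on feasibility". The plan therefore has no figure of its own to reproduce. SAP 6.6 states no test level; two-sided 0.05 is assumed, in line with the MMRM rule ("The confidence coefficient for estimation of confidence interval will be 2-sided 95"%).

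**Inputs assumed.** Mean PGDM change 0, −30 and −50% for placebo, low and high dose, SD 25 points within arm. 6MWD change SD 50 m. High-dose 6MWD effect 30, 50 or 80 m, with half of that at low dose. No PGDM–6MWD association within any arm.

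**Step 1: is pooling the right reading?** Each model has an intercept and five regressors, six parameters. Fitted within one arm it would leave 11 − 6 = 5 residual degrees of freedom; pooled, 33 − 6 = 27. With no instruction to fit by group, pooling is the natural reading.

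**Step 2: how much of PGDM change is arm?** The arm means average −26.67, so the deviations are 26.67, −3.33 and −23.33.

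- Between-arm variance = (711.1 + 11.1 + 544.4)/3 = 422
- Within-arm variance = 25² = 625
- Share due to arm = 422/(422 + 625) = 0.40

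**Step 3: size of the spurious slope.** With no within-arm association, the pooled slope is the between-arm covariance divided by the total PGDM variance. For 0/25/50 m the outcome deviations are −25, 0 and 25.

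- Covariance = (26.67 × −25 + 0 + −23.33 × 25)/3 = −417
- Slope = −417/1047 = −0.40 m per percentage point

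A further 10-point fall in PGDM would thus appear to bring about 4 m, when the true within-arm value is 0.

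**Step 4: how often it reaches significance.** Least squares with the SAP's five regressors, N = 33, simulated:

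| High-dose effect by another route | PGDM term p<0.05, no arm | With two arm indicators |
|---|---|---|
| 30 m | 13% | about 5% |
| 50 m | 26% | about 5% |
| 80 m | 49% | about 5% |

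Repeat runs with these regressors gave 12–13%, 24–26% and 48–49%.

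**Step 5: dependence on the assumed shifts.** The same model in within-arm SD units (low/high dose), no arm term:

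| PGDM shift | Outcome shift 0.25/0.5 | 0.5/1 | 0.75/1.5 |
|---|---|---|---|
| −0.5/−1 | 7% | 12% | 19% |
| −1/−2 | 10% | 25% | 44% |
| −1.5/−3 | 12% | 35% | 63% |

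With arm added, every cell falls to 4–6%. The pooled Pearson correlation behaves much like the unadjusted model (7% to 70%). The rate stays at about 5% without arm when the drug moves only the outcome, only the biomarker, or both out of alignment (for example outcome 0/1/0 against PGDM 0/−1/−2).

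**Step 6: what adjustment costs if PGDM really mediates benefit.** With the same PGDM shifts and SDs and a true slope giving a 50 m high-dose effect (50 m/50 points = 1 m per point), detection is about 90% without arm and 67–68% with it. For a 25 m effect it is 38% and 23%.

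**Step 7: do the per-group correlations settle it?** At n = 11 the critical value is t/√(n − 2 + t²) = 2.262/√(9 + 5.117) = 0.60. Power is about 14% for a true r of 0.3 and 34% for 0.5.

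**The case against.** The strongest reply is that the unadjusted model is not simply wrong. If PGDM lowering is how the drug works, the between-arm variation is real signal, and Step 6 shows that adjusting for arm discards a good part of it. The spurious rates in Step 4 assume instead that the whole benefit comes by an unrelated route, the case least favourable to the plan. This stands, and it is why the remedy is to report both models rather than replace one with the other.

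The plan also already includes per-group correlations, which are free of between-arm confounding. That stands too, although at about 11 boys per arm they can detect only strong associations.

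Further, these are exploratory PPS analyses with no multiplicity adjustment (SAP 3.4.5). Protocol 14.1 looks to numerical trends rather than significance, and 6.6 names P values for the correlations but not for the covariance models. This lowers the severity. It does not remove the point, because the slope itself is distorted (Step 3), not only its P value.

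A reader might infer more than the documents support:

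- **That any drug effect would surface as a biomarker relationship.** It would not: leakage is partial and needs arm shifts in biomarker and outcome that line up.
- **That PGDM change is virtually a label for arm.** Under the assumed inputs arm explains about 40% of its variance.
- **That the 6MWD-on-%MVI model is equally exposed.** That needs a drug effect on %MVI, which no passage establishes.
- **That the creatinine denominator is a second demonstrated fault.** Creatinine excretion is itself an endpoint, but the documents give nothing from which to size a distortion, and total PGDM excretion is already correlated with efficacy changes under SAP 6.3.

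**Conclusion.** The point holds in limited form. Arm is missing from all three covariance models in SAP 6.6. For the two PGDM models, this lets a dose-related effect by another route pass in part into the PGDM coefficient. For 6MWD the spurious significance rate is about 13–49% for high-dose effects of 30–80 m, against about 5% with arm. Across the wider standardised grid it is 7–63%. All shifts and SDs behind these figures are assumptions. The 6MWD simulation was not repeated on the %MVI scale; the standardised grid is the guide there.

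Severity is low to moderate. The primary analysis is untouched, but these models serve a stated exploratory objective and the correction is cheap.

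**What to change.** In SAP 6.6:

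1. Fit both PGDM covariance models with and without assigned group, and do the same for the 6MWD-on-%MVI model for consistency.
2. State in advance that the arm-adjusted coefficient is read as the within-arm association and the unadjusted one as descriptive.
3. Beside each combined-group correlation, report the partial correlation adjusted for assigned group.
4. Optionally, repeat the PGDM models with total urinary tetranor-PGDM excretion, already derived in SAP Table 10.2.

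This changes SAP wording only and needs no new data. The adjusted model uses two more degrees of freedom: 33 − 6 = 27 becomes 33 − 8 = 25 if all boys enter the PPS. The loss is felt more in the 350 m subgroups; a subgroup of 16, assumed for illustration, goes from 10 to 8. The adjusted model also has less power if PGDM truly mediates benefit, and presenting the unadjusted result alongside it covers that case.
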